- Groups A1 and A2 (Normal): patients with normal liver function will be included in this study as matching control patients (Group A1 for Group B and Group A2 for Group C). If the dose for moderate hepatic impairment group (Group C) is selected to be the recommended clinical dose of 100 mg QD, the control group A2 will not be needed to be enrolled. There will be no control group designated to match severe group. However, if a decision has been made to use the same dose for severe and moderate patients, the half of the control Group A2 will be matching Group C and half will be matching Group D.

Child-Pugh scores (criteria listed in Appendix 3) will be calculated and recorded as part of the liver function testing prior to the start of the first lorlatinib dose, but will not be used to stratify patients into treatment groups.

The enrollment of approximately 76 advanced cancer patients is anticipated in this study in order to have 8 PK-evaluable patients in each of Groups A1, A2, B and C, and 6 PK-evaluable patients in Group D for final statistical analysis. Evaluable patients are those who complete the planned PK sample collection on Cycle 2 Day 1 and have no lorlatinib dose modification until completion of Cycle 2 Day 1 PK evaluation. Patients who are not evaluable for PK will be replaced.

Each patient will be treated with repeated oral once daily doses of lorlatinib in 21-day cycles until disease progression, patient refusal, or unacceptable toxicity occurs.

The planned dosing schedule for each treatment group is as follows (Table 4):

	Group B	Group C	Group D	Group A1	Group A2
Hepatic Function	Mild	Moderate	Severe	Normal	Normal
Starting Lorlatinib Dose	100 mg QD	50 mg QD or otherwise determined in the first stage	determined based on preliminary safety and PK data	100 mg QD	the same dose as Group C at the second stage
Lorlatinib Dose After PK Assessment	100 mg QD	50 mg QD or otherwise determined in the first stage	determined based on preliminary safety and PK data	100 mg QD	100 mg QD

Table 4.Lorlatinib Dosing Schedule

The dose schedule may be modified as necessary for individual patients according to tolerability (see Table 6 for detailed dose modification strategy).

For Group C, a two-stage enrollment will be applied.

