# 9.2. Sample Size Determination

The sample size for this study is determined empirically based on feasibility and regulatory recommendation. Sufficient numbers of patients will be enrolled and dosed to obtain approximately 38 PK evaluable subjects (approximately 16 subjects in normal group, 8 patients each in mild and moderate groups, and 6 in severe group).

Subjects may be replaced if not PK evaluable.

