- Groups A1 and A2 (Normal): patients with normal liver function will be included in this study as matching control patients (Group A1 for Group B and Group A2 for Group C). If the dose for moderate hepatic impairment group (Group C) is selected to be the recommended clinical dose of 100 mg QD, the control group A2 will not be needed to be enrolled. There will be no control group designated to match severe group. However, if a decision has been made to use the same dose for severe and moderate patients, the half of the control Group A2 will be matching Group C and half will be matching Group D.

The enrollment of approximately 76 advanced cancer patients is anticipated in this study in order to have 8 PK-evaluable patients in each of Groups A1, A2, B and C, and 6 PK-evaluable patients in Group D for final statistical analysis. Evaluable patients are those who complete the planned PK sample collection on Cycle 2 Day 1 and have no lorlatinib dose modification until completion of Cycle 2 Day 1 PK evaluation. Patients who are not evaluable for PK will be replaced.

Each patient will be treated with repeated oral once daily doses of lorlatinib in 21-day cycles until disease progression, patient refusal, or unacceptable toxicity occurs.

The planned dosing schedule for each treatment group is as follows:

| | Group B | Group C | Group D | Group A1 | Group A2 |
|-----------------|-----------|--------------|-------------|-----------|----------|
| Hepatic | Mild | Moderate | Severe | Normal | Normal |
| Function | | | | | |
| Starting | 100 mg QD | 50 mg QD or | determined | 100 mg QD | the same |
| Lorlatinib Dose | | otherwise | based on | | dose as |
| | | determined | preliminary | | Group C |
| | | in the first | safety and | | at the |
| | | stage | PK data | | second |
| | | | | | stage |
| Lorlatinib Dose | 100 mg QD | 50 mg QD or | determined | 100 mg QD | 100 mg |
| After PK | | otherwise | based on | | QD |
| Assessment | | determined | preliminary | | |
| | | in the first | safety and | | |
| | | stage | PK data | | |

Table 2. Lorlatinib Dosing Schedule

The dose schedule may be modified as necessary for individual patients according to tolerability (see Table 2 for detailed dose modification strategy).

For Group C, a two-stage enrollment will be applied.

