3.4.2.2. PK Parameter Analysis Set

The PK parameter analysis set is defined as all enrolled patients treated who have sufficient information to estimate at least 1 of the PK parameters of interest.

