3.4.2.3. PK evaluable Analysis set

The PK evaluable analysis set is defined as all patients in the PK parameter analysis population who have (1) completed Cycle 2 Day 1 PK collection; (2) received lorlatinib dose on Cycle 2 day 1; (3) received at least 80% of total dose within 14 days prior to Cycle 2 Day 1; (4) no dose reduction in the first cycle.

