4.1. Hypotheses and Decision Rules

The study is not powered to detect treatment difference in PK parameters. No formal statistical hypothesis testing is planned, and no decisions will be made to the conduct of the study.

The sample size for this study is determined empirically based on feasibility and regulatory recommendation. Sufficient numbers of patients will be enrolled and dosed to obtain approximately 38 PK evaluable subjects (approximately 16 subjects in normal group, 8 patients each in mild and moderate groups, and 6 in severe group). Subjects may be replaced if not PK evaluable.

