One-way analysis of variance (ANOVA) will be used to compare the natural log transformed AUC_{24} , AUC_{last} and C_{max} of lorlatinib at steady state for each of the hepatic impairment groups (Test) to the corresponding normal hepatic function group with the same dosing schedule (Reference). Group B (Test) will be compared to Group A1 (Reference) and Group C (Test) will be compared with Group A2 (Reference). If a decision has been made to use the same dose for severe and moderate patients, the half of the control Group A2 will be matching Group C and half will be matching Group D (test), and the corresponding pairwise comparisons will be made. Additionally, Group D will be compared to Group A1 (Reference), and Group C will be compared with A1. Estimates of the mean differences (Test-Reference) and corresponding 90% confidence intervals will be obtained from the

model. The mean differences and 90% confidence intervals for the differences will be exponentiated to provide estimates of the ratio of geometric means (Test/Reference) and 90% confidence intervals for the ratios.

Residuals from the models will be examined for normality and the presence of outliers via visual inspection of plots of residuals vs predicted values and normal probability plots of residuals but these will not be included in the clinical study report. If there are major deviations from normality or outliers then the effect of these on the conclusions will be investigated through alternative transformations and/or analyses excluding outliers. Justification for any alternative to the planned analysis will be given in the report of the study.

The following PK parameters will be summarized descriptively by analyte, hepatic function group and at C1D1 and C2D1 for lorlatinib and its metabolites.

| Parameter | Summary statistics |
|--|--|
| AUC _{24,} AUC _{last} , C _{max} , C _{min} , CL/F, MRAUC _{24,} MRAUC _{last} , MRC _{max} | N, arithmetic mean, median, cv%, standard deviation, minimum, maximum, geometric mean. |
| T _{max} | N, median, minimum, maximum. |

Box and whisker plots for individual subject parameters (lorlatinib AUC $_{24}$, AUC_{last} and C_{max}) will be presented against hepatic function group by analyte and overlaid with geometric means.

PK parameter analysis set will be used for performing the analysis.

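### The primary steady-state ANOVA is assigned to a PK set with no dosing criterion, although the study is sized on PK-evaluable patients; the effect is probably small and a change of SAP wording settles it

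*SAP*

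**What the plan says.** **Sizing.** SAP 2.2 and Protocol 3.1 plan 8 PK-evaluable patients in each of Groups A1, A2, B and C, and "6 PK-evaluable patients in Group D for final statistical analysis". SAP 4.1 adds: "Sufficient numbers of patients will be enrolled and dosed to obtain approximately 38 PK evaluable subjects".

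**Analysis.** SAP 5.1.1.1 compares log AUC24, AUClast and Cmax at steady state between each impaired group and a normal group on the same dosing schedule. It reports ratios of geometric means with 90% confidence intervals. Its last line is "PK parameter analysis set will be used for performing the analysis". A patient belongs to that set by having "sufficient information to estimate at least 1 of the PK parameters of interest" (SAP 3.4.2.2). Protocol 9.3.3 names no set for the ANOVA.

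**The set that is left unused.** The PK evaluable set (SAP 3.4.2.3, Protocol 9.1) requires Cycle 2 Day 1 collection and dosing and that the patient "received at least 80% of total dose within 14 days prior to Cycle 2 Day 1; (4) no dose reduction in the first cycle". Apart from sizing and replacement, its only stated role is to time the first-stage look in Group C (SAP 6).

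**Two wording conflicts.** Protocol 3.1 and SAP 2.2 define evaluable patients as those who complete Cycle 2 Day 1 sampling and "have no lorlatinib dose modification until completion of Cycle 2 Day 1 PK evaluation", which is not the same test as the 80% and no-reduction rule. On replacement, SAP 2.2 says "Patients who are not evaluable for PK will be replaced", while Protocol 9.2 says "Subjects may be replaced if not PK evaluable".

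**The concern.** The primary result is an exposure ratio at a common dose. SAP 4.1 plans no formal test, so the estimate and its interval carry the conclusion. If a patient whose dose was lowered in Cycle 1 still gives a Cycle 2 Day 1 profile, the rule as written admits that profile under the group's nominal dose. A patient below 80% dose intensity who is still sampled is admitted in the same way. In an impaired group this pulls the ratio down and could mask part of an exposure increase; in a control group it pushes the ratio up. Whether such a patient is removed is left to judgement, in an open-label study, after concentrations can be seen.

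**Working it through.** **1. The plan's own figure.** 4 × 8 + 6 = 38, and 16 + 8 + 8 + 6 = 38. The count reproduces, and it is a count of evaluable patients. The number entering the ANOVA on the PK parameter set has no fixed relation to it.

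**2. Does any rule keep the reduced patient out?**

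| Place | Content | Does it settle the matter? |
|---|---|---|
| SAP 4.3.2 | Mandatory removal of known biased estimates, with vomiting as the example | Unclear: a profile at a reduced dose is a valid estimate at that dose |
| SAP 5.4.2.2 | Patients with events affecting PK may be dropped | Discretionary |
| SAP 5 | Splits a group by dose level, with C1/C2 as the example | Placed with summaries; does not say which subgroup enters the contrast |
| SAP 5.1.1.1 | Reference on the same dosing schedule | Selects the reference group, not patients |
| SAP Table 3 | CL/F = Dose/AUC24 | Descriptive; no interval, nothing for Cmax |
| SAP Appendix 2 | Model term is group only | No dose term |

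Patients without a Cycle 2 Day 1 profile drop out anyway. The gap concerns only those who have one.

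**3. How often might this happen?** This is an inference from Protocol Table 2 (Day 15). The geometric mean of a parameter divided by the geometric mean of its dose-normalised value is the geometric mean dose.

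- 75 mg QD: AUCtau 4107/56.62 = 72.5 mg and Cmax 429.6/5.925 = 72.5 mg. One of 12 patients on 50 mg would give 75 × (50/75)^(1/12) = 72.5.
- 100 mg BID: 4058/44.66 = 90.9 mg and 600.5/6.609 = 90.9 mg. One of 3 on 75 mg would give 100 × (75/100)^(1/3) = 90.9.
- 100 mg QD: 5121/51.21 = 100.0 mg. The remaining cohorts also return their nominal dose within 0.4%.

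Profiles: QD 3+3+3+12+16+3+2 = 42 and BID 1+3+3 = 7, so 2 of 49 overall and 1 of 42 on QD.

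**4. Size.** If k of n impaired patients are reduced and r is the exposure ratio of reduced to assigned dose, the group ratio is multiplied by r^(k/n). From Table 2 AUCtau, r = 4107/5121 = 0.802 (100 to 75 mg), 3367/5121 = 0.657 (100 to 50 mg) and 1701/3367 = 0.505 (50 to 25 mg).

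| Rate | 100 to 75 | 100 to 50 | 50 to 25 |
|---|---|---|---|
| 1 of 42 (inferred, QD) | 0.995 | – | – |
| 2 of 49 (inferred, all) | 0.991 | – | – |
| 1 of 9 (assumed) | 0.98 | 0.95 | 0.93 |
| 2 of 10 (assumed) | 0.96 | 0.92 | 0.87 |

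With 2 of 10 controls reduced instead, the factors are 1.05, 1.09 and 1.15.

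**5. Scale.** Take CV 39% (Protocol Table 3, free base, multiple doses), 8 v 8, and four groups of 8, so 28 df. σ = √ln(1 + 0.39²) = 0.376, SE = 0.376 × √(2/8) = 0.188, and log half-width = 1.701 × 0.188 = 0.320. The 90% CI is 0.73 to 1.38 times the estimate. A factor of 0.991 is 0.009/0.320, about 3% of the half-width. The assumed 0.96, 0.92 and 0.87 are 14%, 26% and 43%.

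**6. Does exclusion repair it?** Let s² = ln(1 + CV²), d = log of assigned over reduced dose, and x − m = the reduced patient's log AUC minus the cohort mean. Dose-normalising one patient gives (n−1)(s²after − s²before) = 2d(x − m) + d²(1 − 1/n).

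- 100 mg BID (n = 3, CV 33% to 47%, d = 0.288): 0.192 = 0.575(x − m) + 0.055, so x − m = 0.239. Relative to the dose-corrected mean, keeping the patient gives exp(−0.288/3) = 0.91; excluding gives exp(−0.239/2 − 0.288/3) = 0.81.
- 75 mg QD (n = 12, CV 53% to 48%, d = 0.405): −0.442 = 0.811(x − m) + 0.151, so x − m = −0.731. Keeping gives exp(−0.405/12) = 0.97; excluding gives exp(0.731/11 − 0.405/12) = 1.03.

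**7. Does dose-normalising repair it?** Dose-normalised AUCtau is 67.50 at 50 mg against 51.21 ng·hr/mL/mg at 100 mg, a ratio of 1.318. With 2 of 10 reduced from 100 to 50 mg the AUC24 ratio becomes 1.318^0.2 = 1.06, an over-correction. From 100 to 75 mg it is 1.02 and from 50 to 25 mg 1.00. For Cmax from 50 to 25 mg it under-corrects (0.95).

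**The case against.** The strongest reply is that this is a wording mismatch with little behind it. SAP 4.3.2 is mandatory, SAP 5 heads all analyses and separates dose levels, SAP 2.2 already ties evaluable patients to the final analysis, and CL/F shows AUC24 corrected for dose. Phase 1 reported no dose reductions at 100 mg QD (Protocol 1.2.1.2.1.1), which is the starting dose for Groups A1 and B. Further, on the same Table 2 evidence, exclusion is worse than retention at 100 mg BID and no better for AUC at 75 mg QD.

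Much of this stands. The effect is small at any rate the documents support, and exclusion is not shown to be the more accurate choice. What does not stand is that the text already decides the matter: the one sentence that names a set for this analysis names the PK parameter set, and the other rules are discretionary or unclear for this case.

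Three stronger readings are tempting. A reader might take 0.87 or 0.92 as the expected bias; those need an assumed 2 of 10 reduced. A reader might infer that impaired patients will be reduced more often; that is possible, but the documents give no rate. A reader might infer from about 76 enrolled for 38 evaluable that many non-evaluable patients will enter the ANOVA; the documents do not say why patients would be non-evaluable, and those without a Cycle 2 Day 1 profile cannot enter.

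**Conclusion.** The plan should be corrected as written. Following SAP 5.1.1.1 can mix doses in a ratio that is defined at a common dosing schedule, and the set on which the study is sized serves no final analysis. The likely size is small: a factor of about 0.99 for a one-step reduction from 100 mg at the inferred Phase 1 frequency. That rests on an inference from rounded geometric means in small cohorts (n = 3 at 25 mg, 50 mg and 100 mg BID) and on Phase 1 patients not selected for hepatic impairment.

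It would go too far to say that the primary ratio is materially biased, or that moving to the evaluable set yields the unbiased answer. Exclusion can remove high exposures (0.81 against 0.91 at 100 mg BID), and dose-normalising can over-correct because exposure is less than dose-proportional. The two analyses show sensitivity; they are not guaranteed to bracket the true ratio.

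The evaluability and replacement conflicts are separate. They need reconciling so that one definition governs replacement and analysis, but they are not evidence of bias.

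**What to change.** Replace the last sentence of SAP 5.1.1.1 with:

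> The steady-state ANOVA of AUC24, AUClast and Cmax uses the PK evaluable analysis set. Listings and descriptive summaries use the PK parameter analysis set. The same ANOVA is reported beside it, with equal prominence, for all patients with a Cycle 2 Day 1 profile, with each parameter normalised to the dose actually taken. Every patient excluded from the first analysis is listed with group and reason. Neither analysis is unbiased: exclusion can remove high exposures, and dose-normalising can over-correct.

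Separately, reconcile the evaluability definition in Protocol 3.1 and SAP 2.2 with that in Protocol 9.1 and SAP 3.4.2.3, and make replacement either mandatory or optional throughout.

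The cost is SAP wording, a short protocol clarification and one extra ANOVA run; no new data are needed. If excluded patients are not replaced, precision falls slightly. At 6 v 8 (26 df, CV 39%) the log half-width is 1.706 × 0.376 × √(1/6 + 1/8) = 0.347, so the 90% CI is 0.71 to 1.41 times the estimate, against 0.73 to 1.38 at 8 v 8.

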5.1.1.2. Pharmacokinetic Concentration Analysis Methods

Presentations for lorlatinib and its metabolites concentrations will include:

- listings of all plasma concentrations sorted by analyte, hepatic function group (present in heading), cycle, subject id and nominal time postdose. The listing of plasma concentrations will include the actual times. Deviations from the nominal time will be given in a separate listing.
- summaries of plasma concentrations by analyte, hepatic function group, cycle and nominal time, where the set of statistics will include n, mean, median, standard deviation, geometric mean, coefficient of variation (cv), minimum, maximum and the number of concentrations above the lower limit of quantification.

- median plasma concentrations time plots (on both linear and semi-log scales) against nominal time postdose by analyte, hepatic function group and cycle (all cycles on the same plot for each hepatic function group per scale per analyte, based on the summary of plasma concentrations by analyte, hepatic function group, cycle and time postdose).
- mean plasma concentrations time plots (on both linear and semi-log scales) against nominal time postdose by analyte, hepatic function group and cycle with one side up standard deviation (all cycles on the same plot for each hepatic function group per scale per analyte, based on the summary of plasma concentrations by analyte, hepatic function group, cycle and time postdose).
- individual plasma concentration time plots against actual time postdose by analyte, hepatic function group and cycle (on both linear and semi-log scales), (there will be separate spaghetti plots for each hepatic function group per scale and will be different lines for each cycle on the same individual plots).
- median plots of the predose concentrations against day (including day 1 of cycle 2 as Day 29 on the same x-axis) by analyte and hepatic function group in order to assess the attainment of steady-state (all hepatic function group on the same plot),
- individual plots of the predose concentrations against day (including day 1 of cycle 2 as Day 29 on the same x-axis) by analyte and hepatic function group.

For summary statistics, median and mean plots by sampling time, the nominal PK sampling time will be used. For individual subject plots by time, the actual PK sampling time will be used.

PK concentration analysis set will be used for performing the analysis.

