Serious and non-serious adverse event monitoring 	Х	$\rightarrow$	$\rightarrow$	$\rightarrow$	$\rightarrow$		$\rightarrow$	$\rightarrow$	Х
Concomitant treatment(s) 	Х	$\rightarrow$	$\rightarrow$	$\rightarrow$	$\rightarrow$		$\rightarrow$	$\rightarrow$	Х
Suicidal Ideation and Behavior 		Х			Х		X (up to Cycle 6 and then Day 1 of every other cycle)	Х	
Other assessments									
Pharmacokinetics 		Х	Х	Х	Х				
CCI									

Abbreviations:  $\rightarrow$  = ongoing/continuous event; CT = computed tomography; ECG = electrocardiogram; ECOG = Eastern Cooperative Oncology Group; ECHO = echocardiogram; HBV = hepatitis B virus; HCV = hepatitis C virus; LVEF = left ventricular ejection fraction; MRI = magnetic resonance imaging; MUGA = multigated acquisition scan; RECIST= Response Evaluation Criteria for Solid Tumors. (X) – to be completed if not performed within 7 days of the first dose of lorlatinib.

- a. Day relative to start of study treatment (Day 1).
- 1. Screening: To be obtained within 28 days prior to the start of study treatment.
- 2. Study Treatment: All assessments should be performed prior to dosing with lorlatinib unless otherwise indicated. Acceptable time windows for performing each assessment are described in the column headers. All cycles are 21 days in duration. Following completion of Cycle 2, ongoing patients on lorlatinib will need to visit the clinic on Day 1 of every cycle for assessments. Enough study medication for one cycle of treatment will be dispensed at each clinic visit. Some assessments such as Liver Function Assessment and physical examination could be performed more frequently at the discretion of investigator according to the standard practice at the site. Tumor assessments may occur at every odd-numbered cycle or according to standard practice for the indication at the site.
- 3. Cycle 1/Day 1: Blood chemistry, hematology, coagulation, lipids, and physical examination not required if acceptable corresponding screening assessment was performed within 7 days prior to the start of study treatment. Values closest prior to the first dose of lorlatinib will be used for baseline.
- 4. Informed Consent: Must be obtained prior to undergoing any study-specific procedures.

- 5. Medical/Oncological History: To also include information on prior medications, smoking history, prior treatment regimens. Will be updated on Cycle 1 Day 1 before the start of treatment.

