## 5.4. Administration

All trial treatments will be administered on an outpatient basis.

A cycle is defined as 21 days, irrespective of any dose delays/dosing interruptions or missed doses which may affect nominal days of each cycle.

Lorlatinib will be administered orally QD at approximately the same time of the day on a continuous daily dosing schedule, ie, without a break in dosing in the absence of drug-related toxicity. Patients must swallow the study medication whole and must not manipulate or chew the medication prior to swallowing. A dosing card will be provided to the patients to provide guidance for the correct use of lorlatinib. Patients must be instructed that should they miss a dose or vomit any time after taking a dose, they must not "make it up" with an extra dose. Instead, resume the subsequent doses as originally prescribed. Any missed dose may be taken up to 6 hours prior to the next scheduled lorlatinib dose, otherwise it should be skipped and dosing resumed with subsequent doses as prescribed. The patient must be instructed to record all doses (including missed or vomited) in a dosing diary supplied by the site. If doses are missed or vomited, this must be indicated in the source documents and Case Record Forms (CRFs).

On PK sampling days, the lorlatinib dose should be taken in the clinic under the supervision of the study site personnel. The lorlatinib dose should be administered after the 0 hour (predose) PK sample has been collected (within 15 minutes prior to lorlatinib dosing). On ECG assessment days, the lorlatinib dose should also be taken in the clinic under the supervision of the study site personnel so that timing of assessments is appropriately synchronized.

Since no clinically meaningful effect of food on the PK of lorlatinib has been observed, lorlatinib can be administered with or without food.

Lorlatinib treatment may continue until confirmation of disease progression, patient refusal, or unacceptable toxicity despite of dose reduction or interruption, whichever occurs first.

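### The SAP's predose plots place Cycle 2 Day 1 at Day 29, but with 21-day cycles it is Day 22, so the last interval on the steady-state plot is drawn at twice its length

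*SAP*

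**What the plan says.** SAP 5.1.1.2 lists the concentration displays, and two of its bullets concern predose values. The first describes a median plot, with the instruction "including day 1 of cycle 2 as Day 29 on the same x-axis". It is split by analyte and liver-function group, and its purpose is given: "in order to assess the attainment of steady-state". The next bullet asks for "individual plots of the predose concentrations against day (including day 1 of cycle 2 as Day 29 on the same x-axis", and states no purpose.

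The section closes with a rule on time axes: nominal times for summaries and for median and mean plots, actual times for individual plots by time.

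On cycle length the documents agree with one another:

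- SAP 2.2: "Each patient will be treated with repeated oral once daily doses of lorlatinib in 21-day cycles".
- Protocol Schedule of Activities, footnote 2: "All cycles are 21 days in duration".
- Protocol 5.4: "A cycle is defined as 21 days, irrespective of any dose delays/dosing interruptions or missed doses".

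The Schedule of Activities also fixes the origin of the day count: "Day relative to start of study treatment (Day 1". Its footnote 21 puts predose samples on Cycle 1 Days 1, 8 and 15 and on Cycle 2 Day 1.

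**The concern.** Day 29 is where Cycle 2 would begin if cycles lasted 28 days, and no part of either document uses a 28-day cycle. A programmer who follows the SAP literally would put the fourth predose point a week too far to the right.

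That point matters to what the plot is for. The primary endpoints are AUC24 and Cmax at steady state, taken from the Cycle 2 Day 1 profile. The predose value on Cycle 1 Day 1 precedes the first dose, so the plot informs on steady state through the Day 8, Day 15 and Cycle 2 Day 1 troughs. The segment that runs into the primary PK day is the one that is stretched, and stretching makes a trough that is still moving look flatter. Protocol 1.2.2 says that lorlatinib's effect on its own metabolism may differ in hepatic impairment, so it is reasonable to want this picture drawn correctly in each group.

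**Working it through.** **Inputs.** Cycle length L = 21 days (SAP 2.2; Protocol Schedule of Activities and 5.4). Day 1 is the start of treatment. Cycle 1 predose samples fall on Days 1, 8 and 15. The visit window for Day 15 and for Cycle 2 Day 1 is ±2 days (Schedule of Activities).

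**Can Day 29 be reproduced?** The study day of Cycle 2 Day 1 is L + 1.

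- L = 21: 21 + 1 = 22.
- L = 28: 28 + 1 = 29.
- L = 21 with the visit window: 22 − 2 = 20 to 22 + 2 = 24.

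Only a 28-day cycle gives 29. As a cross-check, SAP 5.2.2 equates imaging at odd-numbered cycles with 6 weeks: 2 × 21 = 42 days = 6 weeks, whereas 2 × 28 = 56 days = 8 weeks. The SAP therefore works with 21-day cycles elsewhere too.

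**Effect on the axis, nominal days.**

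| Segment | True length (days) | Length as drawn (days) |
|---|---|---|
| Day 1 to Day 8 | 8 − 1 = 7 | 7 |
| Day 8 to Day 15 | 15 − 8 = 7 | 7 |
| Day 15 to Cycle 2 Day 1 | 22 − 15 = 7 | 29 − 15 = 14 |

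**Effect on apparent slope.** Let Δ be the change in trough from Day 15 to Cycle 2 Day 1. The true slope is Δ/7 per day and the drawn slope is Δ/14, so the ratio is (Δ/14)/(Δ/7) = 7/14 = 0.5. The two earlier segments keep their true slope, so the last one looks flatter relative to them as well. Δ itself does not change.

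**Individual patients.** The factor of two is exact for nominal days only. With Day 15 falling on Days 13 to 17 and Cycle 2 Day 1 on Days 20 to 24, a patient's true interval runs from 20 − 17 = 3 to 24 − 13 = 11 days. A fixed 14-day gap would overstate it by a factor between 14/11 = 1.3 and 14/3 = 4.7. If actual times are used, the point falls near Day 22 and this distortion does not arise.

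**The case against.** The other side grants the error and disputes its reach. Most of what it says stands, and it rules out five stronger readings that a reader might infer.

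- **That this is the only evidence on steady state.** It is not. The same section requires listings of all concentrations with actual times, and summaries by group, cycle and nominal time. These show the predose values and do not depend on the label. The median plot is the only output labelled for this purpose, which is a narrower statement.
- **That both plots carry the steady-state purpose.** The SAP attaches it to the median plot alone.
- **That the slope is halved in every patient's plot.** The documents leave this open. The individual bullet says Day 29, but the section's closing rule calls for actual times in individual plots by time. The two instructions conflict, and the SAP does not say which governs.
- **That the primary result is affected.** AUC24 and Cmax come from sampling times relative to the Cycle 2 Day 1 dose. The ANOVA and the 90% intervals use no study-day label. No slope is estimated, no steady-state test is specified, and no patient is excluded on the basis of the plot.
- **That steady state is in doubt in these patients.** Protocol 1.2.1.2.1.1 says that in the earlier patient study steady state should have been reached before Day 15. For impaired patients, the protocol says only that the effect on metabolism may differ, and it gives no time to steady state for them.

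A reader who compares the heights of the last two troughs will see the right difference. What does not stand is any defence of the number itself. The visit window stops at Day 24. An out-of-date protocol version cannot explain it either, because the SAP states 21-day cycles in its own text.

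**Conclusion.** The instruction is wrong as written: Cycle 2 Day 1 is nominally Day 22, and Day 29 is seven days late. On the nominal-time median plot the last interval is drawn at twice its length, and any remaining trend is shown at half its slope, in the direction that favours accepting steady state. For the individual plots the finding is an internal conflict between the Day 29 label and the actual-time rule, not a certain distortion.

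The conclusion rests on the 21-day cycle and on counting from the first dose as Day 1, both of which the documents state. The exact factor of two rests on nominal days. This is a minor error in a descriptive figure. It is worth correcting because it sits in the one display given the task of judging steady state, but it changes no estimate, interval or analysis set.

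**What to change.** In SAP 5.1.1.2, replace Day 29 with Day 22 in the median-plot bullet and in the individual-plot bullet. Alternatively, for the individual plots, drop the fixed day and plot predose values against actual study day, which also removes the conflict with the section's closing rule.

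The cost is one number in two bullets and the matching axis setting in the figure programs. Design, data collection, sample size and the primary analysis stay as they are.
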